#### **12.3.1 Bilateral Frontal SBD**

Confirm bilateral FSO access and complete bilateral in-office dilation per the Cube Navigation System, VenSure™ Nav Balloon Device, and Inflation Device IFUs. If the eligibility CT Scan does not meet the Cube Navigation System requirements, the CT Scan may need to be re-done.

Subjects may be asked to take off their mask (just like earrings, glasses, etc.,) for the few seconds during which the CT scan is captured to maximize accuracy with the navigation system.

Prior to implant placement:

- Confirm successful bilateral frontal SBD with an opening amendable for PROPEL Contour placement on each side.
- Evaluate final subject eligibility by confirming that the subject's anatomy and overall condition is appropriate for PROPEL Contour placement.

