6.7 Missing Data for Efficacy and Safety Endpoints

Missing data for each efficacy endpoint will be handled as described in Sections 9.1 and 9.3.4.

For continuous endpoints, change from baseline will be set to missing at visits with missing postbaseline values or where data were imputed to missing. Continuous efficacy endpoints will be set to missing for subjects who received any of the following not allowed medication post-baseline procedure:

- Corticosteroids (e.g., oral, parenteral or injection, budesonide or other sinus steroid irrigations/rinses or drops, breath powered Xhance, nebulized steroids administered nasally or other drug eluting stents) through Day 45; or
- Biologics for CRS treatment (e.g., Dupixent).

For binary endpoints, subjects with missing efficacy data, early withdrawals, and/or subjects who received not allowed corticosteroids or biologics for chronic sinusitis condition attributable to the FSO/frontal recess will be imputed as a treatment failure. If a subject initiates high-dose steroid for other reasons not involving FSO/frontal recess, this does not represent treatment failure.

Additional rules for handling of missing data and rescue treatments are detailed below:

- *Missing efficacy data.* Visits with missing data (due to a missed visit or missing component of a composite endpoint) will be set to treatment failure.
- *Early withdrawals.* Only visits following the early withdrawal visit will be set to treatment failure.
- *Rescue treatments.* Subjects who rescue with corticosteroids (before Day 45) or biologics will be set to treatment failure at all subsequent visits and continuous endpoints set to missing.
- *Missing baseline value.* For efficacy endpoints, a missing value at baseline will not be imputed, and the endpoint will be set to missing for all visits.

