9.2.3 Need for Post-operative Intervention

Need for post-operative intervention is determined by clinical investigators at Day 21, 45, 90, and 180 as follows:

- Repeat frontal BSD warranted or performed for restenosis/occlusion in the frontal recess/FSO; or
- Surgical intervention warranted or performed to debride obstructive adhesions/scarring or for restenosis/occlusion in the frontal recess/FSO; or
- Oral steroids warranted or prescribed to resolve recurrent edema in the frontal recess/FSO.

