9.3.1 Definition

The cross-sectional area will be determined by the independent, blinded reviewer on CT at Day 45 within the mucosa at the location of the measured minimum diameter between 5 mm superior and 5 mm inferior to the ostium. It will be reported in mm² for the left and right ostia separately.

For each subject, the difference between FSO cross-sectional area at Day 45 in the treatment and control sides will be calculated and then averaged across all subjects in the ITT population. The FSO cross-sectional area will be set as missing if the FSO is unable to be viewed or measured.

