9.3.2 Statistical Hypothesis

The primary efficacy hypothesis is that the placement of the PROPEL Contour will significantly increase the FSO cross-sectional area on the treatment side versus the control side. The relevant null and alternative hypotheses for this primary efficacy endpoint are:

$$H_0: \mu = 0$$

$$H_1: \mu \neq 0$$

Where μ represents the mean difference between the treatment and control sides in cross-sectional area of the FSO at Day 45.

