9.3.3 Primary Analysis

The primary statistical method is a t-test comparing the mean FSO cross-sectional area at Day 45 in the treatment and control sides.

The study will be considered successful if there is a statistically significant difference in mean FSO cross-sectional area in favor of the treatment side. Although the alternative hypothesis is two-sided, only a statistically significant difference in average FSO area favoring the treatment side will constitute evidence of effectiveness.

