9.3.4 Sensitivity Analyses

Sensitivity analysis for medical or surgical intervention

Because intervention with oral steroids or surgical intervention may confound the primary efficacy endpoint, the following method will be applied to the analyses in cases where such interventions are performed:

- If a subject initiates oral steroids or undergoes revision ESS for CRS conditions attributable to the FSO/frontal recess before Day 45, this represents treatment failure. If the intervention occurs on the treatment side or both sides, the FSO cross-sectional area of the treatment side will be imputed with the value of the control side (i.e., side-to-side difference in FSO area is

zero). If the intervention occurs on the control side only, the FSO cross-sectional area in the control side will be imputed as zero (i.e., totally occluded).

- If a patient initiates oral steroids for other reasons not involving the FSO/frontal recess before Day 45, this does not represent treatment failure. In this scenario, the side-to-side difference in FSO cross-sectional area for that subject will be imputed as zero.
- No other data imputation rules will be applied in the planned statistical analyses.

Sensitivity analysis for missing data

Subjects with a missed visit, lost to follow-up, or with FSO cross-sectional area ‘unable to view’ by the independent, blinded reviewer will be considered as missing data. If more than 10% of the primary efficacy data are missing, the following imputation analyses will be performed to test the robustness of the primary efficacy conclusion in order:

- *Worst-case imputation.* The worst case of side-to-side difference in FSO area is zero. If the primary efficacy endpoint passes (p -value < 0.05) using worst-case imputation, then there is no need to do a best-case imputation analysis.
- *Best-case imputation.* The best case of side-to-side difference in FSO area is equal to the average for the treatment site.

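### SAP 6.7 sets an efficacy endpoint to missing at every visit when its baseline is missing, which, read literally, discards readable Day 45 values from analyses that use no baseline and conflicts with SAP 6.1, 9.3.1 and 9.3.4

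*SAP*

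**What the plan says.** The last bullet of SAP 6.7, in a list introduced as additional rules, reads: "For efficacy endpoints, a missing value at baseline will not be imputed, and the endpoint will be set to missing for all visits". It names efficacy endpoints in general and makes no exception for the primary endpoint.

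The primary endpoint is built from Day 45 values alone. SAP 9.3.1: "For each subject, the difference between FSO cross-sectional area at Day 45 in the treatment and control sides will be calculated". In SAP 9.3.2 the parameter μ "represents the mean difference between the treatment and control sides in cross-sectional area of the FSO at Day 45". SAP 9.3.3: "The primary statistical method is a t-test comparing the mean FSO cross-sectional area at Day 45 in the treatment and control sides". There is no baseline term in the endpoint, the hypothesis or the test.

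Of the five key secondary endpoints in SAP 9.4 and 9.4.1, only the first is a change from baseline. Numbers 2 to 4 (outflow tract volume, minimum diameter, Zinreich score) are Day 45 values compared between sides.

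A baseline for the CT measures does exist. SAP 6.2 takes the last observation before study treatment, and SAP 6.4 has the core lab read the Screening CT as well as the Day 45 and Day 180 scans. A baseline area can therefore be missing and trigger the rule.

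Other text treats missing data differently:

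- SAP 9.3.1: "The FSO cross-sectional area will be set as missing if the FSO is unable to be viewed or measured".
- The missing-data part of SAP 9.3.4 covers "Subjects with a missed visit, lost to follow-up, or with FSO cross-sectional area" that the blinded reviewer could not view. A missing baseline is not among these categories.
- SAP 6.1 presents all data available at each time point.
- SAP 6.7 itself opens by sending the reader to 9.1 and 9.3.4, neither of which mentions a missing baseline.

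**The concern.** A rule suited to change scores is worded to cover every efficacy endpoint. Elsewhere in SAP 6.7, where the authors mean change from baseline only, they say so, so the broader wording cannot simply be assumed to mean the same.

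Two things are at stake. Taken literally, the bullet removes randomised subjects with complete outcome data from the ITT analysis, for a reason unconnected with the outcome. And because the endpoint-specific sections point the other way, two programmers working from the same SAP could build different primary analysis sets. SAP 5.2 breaks the blind for the Day 45 primary analysis, so if the question surfaces only then, it would be settled with results in view.

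**Working it through.** **1. One subject, two readings.** Take a subject whose Screening area could not be read on one side, but whose Day 45 areas A_T (treatment) and A_C (control) are both readable.

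| Source | Consequence for the primary endpoint |
|---|---|
| SAP 6.7, last bullet, taken literally | Missing at all visits; subject drops out |
| SAP 9.3.1 | Both areas were viewed and measured, so D = A_T − A_C is used |
| SAP 9.3.4 | Not a missed visit, loss to follow-up or unviewable area, so not missing |
| SAP 6.1 | Available Day 45 data are presented |

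The same split arises for key secondary endpoints 2 to 4. For key secondary 1 the value is missing on either reading, and rightly so, because it cannot be computed without a baseline.

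**2. The plan's own sample size.** Inputs from SAP 4.4: mean difference 9 mm², SD of the side-to-side difference 18 mm², two-sided alpha 0.05, target power 95%, 56 evaluable subjects, a 20% non-evaluable allowance and 80 randomised. For a paired t-test on n differences:

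noncentrality = (9/18)·√n, df = n − 1

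power = 1 − F(t₀.₉₇₅) + F(−t₀.₉₇₅), where F is the noncentral t distribution function.

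- n = 56: 95.7%, so the plan's statement of at least 95% is reproduced.
- n = 54: 95.0%, the smallest n that meets the target. At n = 53 power is 94.7%.
- n = 64, which is 80 × 0.80: 97.6%.

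**3. What the rule could cost.** The documents give no rate of missing baseline areas. The shares below are assumptions, applied to subjects otherwise evaluable at Day 45, with no overlap with other losses, and rounded down.

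| Assumed share with a missing baseline | Pairs left of 64 | Power |
|---|---|---|
| 0% | 64 | 97.6% |
| 5% | 60 | 96.8% |
| 10% | 57 | 96.0% |
| 15% | 54 | 95.0% |
| 20% | 51 | 93.8% |
| 30% | 44 | 90.0% |

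Power stays at or above 95% until more than 64 − 54 = 10 further pairs are lost, and 10/64 is about 16%. If only the planned 56 pairs were otherwise evaluable (all 24 extra subjects lost), the margin is smaller: 5% leaves 53 pairs (94.7%) and 10% leaves 50 (93.4%). With the bullet confined to change scores, the rule removes no Day 45 pairs.

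**4. Link to the sensitivity analysis.** SAP 9.3.4 starts its imputation analyses when more than 10% of primary data are missing, that is, more than 8 of 80. The plan does not say whether pairs removed by the 6.7 bullet count towards the 8. Nor does it say whether the worst-case step would then put zero in place of a side-to-side difference that was actually observed.

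**The case against.** The strongest reply is that the endpoint-specific text governs. SAP 6.7 defers at the outset to 9.1 and 9.3.4, the disputed bullet comes last, and 9.3.1 and 9.3.4 define missingness for the primary endpoint without reference to baseline. A sensible programmer could well keep the Day 45 pair. This stands in part: deletion is the literal reading, not a certainty. But the bullets are offered as additional to the sections cited, no order of precedence is given, and the bar in 9.3.4 on further imputation rules does not clearly cover setting a value to missing.

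The second reply is that few subjects would be affected. The Screening CT is an eligibility requirement and is to be uploaded for central review (Protocol 7 and 11.1; SAP Appendix A). Protocol 12.3.1 adds: "If the eligibility CT Scan does not meet the Cube Navigation System requirements, the CT Scan may need to be re-done". That sentence concerns navigation, so it does not guarantee that the core lab can read the scan, but it gives no support to a high missing rate either. This reply stands: the number may be small or zero.

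Three stronger readings are tempting but not supported:

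- *The need-for-intervention endpoint becomes missing for everyone.* SAP 9.2.3 says: "Need for post-operative intervention is determined by clinical investigators at Day 21, 45, 90, and 180 as follows". No baseline value is due, so none is missing, and SAP 6.7 has its own treatment-failure rule for missing binary data.
- *The loss falls on the most obstructed ostia and shifts the estimate towards milder disease.* Lund-Mackay grades opacification of the sinus, not whether the ostium can be measured. SAP 9.3.4 equates total occlusion with an area of zero, so a closed ostium might be recorded as 0 mm² and not as missing. The measurement protocol is CP-00038, which is not among the documents.
- *Falling below 56 subjects loses the planned power.* Power is still 95.0% at 54.

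**Conclusion.** The rule is wrong as written and should be fixed. As worded, it removes readable Day 45 values from the primary endpoint and from key secondary endpoints 2 to 4, none of which uses baseline, and it contradicts SAP 6.1, 9.3.1 and 9.3.4 with no stated precedence. The supported harm is the discarding of observed ITT outcomes and an ambiguous primary analysis set, including how the 10% trigger is counted.

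The size is unknown. On the SAP 4.4 assumptions with 64 evaluable pairs, an assumed loss of up to 10 pairs keeps the 95% target. A shortfall requires either a larger loss or a starting point near the planned 56, and the documents support neither as an expectation. A reader might infer a loss of power or a bias towards milder disease; neither is shown.

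**What to change.** Before the Day 45 unblinding, replace the last bullet of SAP 6.7 with wording such as:

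> A missing baseline value is not imputed; only change-from-baseline variables are set to missing. Observed post-baseline values are used in all analyses that do not involve baseline, including the primary endpoint and key secondary endpoints 2 to 4.

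In SAP 9.3.4, add that a missing baseline does not count as missing primary data, either for the 10% trigger or for the worst-case and best-case imputations.

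The cost is two short SAP edits. No new data are needed, sample size and test are unchanged, and key secondary 1 is handled as before.

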6.8 Multiple Assessments and Visits

If a variable (e.g., CT) has been assessed multiple times at the same visit, only the last assessment will be used.

Only completed scheduled visits will be included in summary tables (**Appendix B**). Listings will include scheduled and unscheduled visits (**Appendix C**).

6.9 Data Assurance

All tables, figures and data listings to be included in the report will be independently checked for consistency and integrity in accordance with the study sponsor's SOPs.

6.10 Consistency Across Study Centers

The consistency of device performance across the study centers will be investigated. A one-way analysis of variance (ANOVA) will be used to test whether the mean difference in FSO area between treatment and control sides differs by site. If a statistically significant site effect is not found (at the 0.15 significance level, i.e., $p \geq 0.15$), results will be considered poolable across sites. If a statistically significant site effect is found ($p < 0.15$), exploratory analyses will be conducted to investigate the issue. This may include regression adjustment for baseline clinical characteristics; the set of baseline characteristics to be considered include those that significantly differ across sites, or significantly predict the difference in FSO area between the treatment sides.

If regression adjustment causes the site term to become non-significant, results will be considered poolable across sites, and covariate-adjusted estimates of the treatment effect will be reported. If regression adjustment does not explain the site heterogeneity, further summaries (separating sites or excluding sites) will be explored.

6.11 Coding Dictionaries

Each AE will be coded using the Medical Dictionary for Regulatory Activities (MedDRA, version 24.0 or later). Prior and concomitant medications will be coded using the March 2018 or later version of the World Health Organization (WHO) Drug Global dictionary.

7 SUBJECT ENROLLMENT AND DISPOSITION

The number and percentage of subjects in whom the implant procedure was attempted and in whom it was successful will be summarized. The primary reason for subject discontinuation will be summarized. Screen failures will be reported in the data listings and the summary table. Data for subject disposition, including termination date and reason, will be listed. The randomization schedule used for the study will be provided in a listing and as an appendix to CSR.

8 DEMOGRAPHICS AND BASELINE CLINICAL CHARACTERISTICS

Demographic data (i.e., age, gender, race, ethnicity) and baseline clinical characteristics (i.e., CRS diagnosis, CRS symptoms present for at least 12 weeks, number and extent of prior endoscopic sinus surgery, current status of asthma and allergic rhinitis diagnosed by physician, aspirin intolerance or allergy, any allergies, and history of smoking, history of repeated courses of corticosteroids and history of epistaxis) will be presented for all subjects. Baseline Lund-Mackay score and endoscopic scorings will be summarized per treatment side.

9 EFFICACY ANALYSES

9.1 General Considerations

Missing data imputation analyses:

- *Observed case (OC)*. Missing values remain missing. For the categorical composite endpoints, in the case that some components are missing, the composite endpoint assessment will be derived based on the non-missing components. If non-missing components are not sufficient to determine final composite endpoint, then the composite endpoint will be set as missing. For continuous composite endpoints, if any components are missing, the composite endpoints will be set as missing.
- *Last observation carried forward (LOCF)*. Baseline measurements will not be carried forward to post-baseline. Only post-baseline measurements will be LOCF. For the composite

endpoints, the last non-missing post-baseline observation will be carried forward to subsequent visits for each individual component first, and then the composite endpoints using individual components imputed by LOCF will be calculated as described above. If a subject does not have a non-missing observed record for a post-baseline visit, the last post-baseline record prior to the missed visit will be used for this post-baseline visit. If the last non-missing observation prior to the missing visits cannot be determined due to multiple measurements occurring at the same time or the time not available within the same day, the worst outcome will be used for LOCF. If missing components still exist after LOCF, the composite endpoints will be calculated using the same rules as described in OC.

- *Non-responder imputation (NRI)*. For all binary response measurements, starting from OC, all missing values will be set as non-responders. If subject only had baseline measurements, LOCF and OC analyses will not include this subject. But this subject will be treated as non-responder in NRI analyses.

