### 21.1 Study Procedures During COVID-19

- The implementation of contingency measures should be consistent with the protocol to the extent possible, and sponsor and clinical investigators should document the reason for any contingency measures implemented.
- Informed consent and Screening: The ICF may be sent to prospective subjects for review and discussed remotely via phone contact or virtual visit but it must be signed and dated during on-site visit prior to and on the same day as the protocol-required screening assessments to confirm initial eligibility and obtain baseline values. In the event that new information requires a subject be re-consented, the updated ICF may be sent to the subject electronically or via mail for review and discussed remotely via phone contact or virtual visit. The consent form can be signed, scanned and returned electronically to the site, returned by mail using a

prepaid envelope provided by the site, or returned in person. COVID-19 screening procedures that may be mandated by the clinical sites do not need to be entered into EDC. If a potential subject tests positive for COVID-19, the subject is considered screen failure.

- Follow-up Visit: If COVID-19 restrictions or subject's health status prevent the subject from attending a protocol-required on-site visits, those visits can be conducted remotely. The protocol-required CT and endoscopic assessment on baseline and follow-up visits shall be conducted on-site to maintain data quality and integrity for the primary and key secondary efficacy endpoints. If a subject completes the follow up visits out of window because of COVID-19, this will be reported as a protocol deviation with COVID-19 as a reason. The data from these late visits can be leveraged based on scientifically based rationale and clinical judgement.
- CT and endoscopy assessment: If the CT or endoscopy assessment cannot be completed within the visit window, they can either be completed within reasonable (< 30 days) from the visit window or be left as not done. These will be reported as a protocol deviation with COVID-19 as a reason.
- SNOT-22, RSI and CRS side-specific symptom questionnaire: The study staff can mail the paper questionnaires to the subject's home for completion during a virtual study visit. The completed and initialed questionnaires can be returned to the site in person or using envelopes provided by the study site. The visit type will be recorded in the EDC.

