6 STATISTICAL METHODS

6.1 General Considerations for Data Analysis

All analyses described in this plan are considered a priori analyses in that they have been defined prior to locking the database and reviewing unblinded results. All other analyses, if any, designed subsequent to locking the database will be considered post-hoc analyses and will be considered exploratory. Any post hoc analyses will be clearly identified in the clinical study report.

Continuous data such as cross-sectional area of FSO, FSO minimum diameter, FSOT volume, inflammation score, CRS side-specific symptom score, SNOT-22 score, and RSI score will be summarized in terms of the mean, standard deviation (SD), median, minimum, maximum, and number of observations, unless otherwise stated.

Categorical data such as Lund-Mackay score, Zinreich's modified Lund-Mackay score, adhesion/scarring grade, polypoid edema grade, and polyp grade will be analyzed quantitatively and summarized in terms of the mean, standard deviation (SD), median, minimum, maximum, and number of observations, unless otherwise stated.

Categorical data such as need for post-operative intervention in the frontal recess/FSO, patient satisfaction, implant delivery success rate, and economic measures will be summarized in terms of the number of subjects providing data at the relevant time point, frequency counts and percentages. If not stated otherwise, percentages will be presented with one decimal place. Percentages will not be presented for zero counts. Percentages will be calculated using n as the denominator. 100% will be presented without decimal places. Frequency distributions showing

findings by treatment side will be presented with counts, percentages and, where appropriate, exact 95% CI using the Clopper and Pearson method.

P-values greater than or equal to 0.001, in general, will be presented to 3 decimal places. P-values less than 0.001 will be presented as “< 0.001”.

95% Confidence intervals (CI) will be presented to 1 more decimal place than the raw data. Unless stated otherwise, a two-sided 95% confidence level will be calculated when confidence interval is presented.

Data from the protocol-specified visits (i.e., as reported in the case report form, CRF) will be used in the summary tables and data listings.

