All statistical tests will be two-sided and interpreted at a 5% significance level. A p-value < 0.05 will be considered statistically significant. Unless stated otherwise, a two-sided 95% CI will be calculated and presented.

All available data at each time point will be presented. No imputations for missing data are planned, unless indicated otherwise.

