9.2.4 Patient-Reported Outcomes

9.2.4.1 SNOT-22 Questionnaire

The Sino-Nasal Outcome Test (SNOT-22) questionnaire is a validated, disease-specific, symptom-scoring instrument consisting of 22 questions, each scored by patient on a 6-point scale as follows:

- 0: No problem
- 1: Very mild problem
- 2: Mild or slight problem
- 3: Moderate problem
- 4: Severe problem
- 5: Problem as bad as it can be

The maximum total score for all symptoms is equal to 110. The total SNOT-22 scores and individual domain scores will be computed. The total score is calculated as the sum of all 22 items, and ranges from 0 to 110, with the higher scores being worse outcome. The following **Table 3** lists items and ranges for each symptom domain score.

Table 3: SNOT-22 Domain Scoring

SNOT-22 Domain	Survey Item	Score Range
Rhinologic Symptoms	1, 2, 3, 6, 21, 22	0–30
Extra-Nasal Rhinologic Symptoms	4, 5, 6	0–15
Ear/Facial Symptoms	2, 7, 8, 9, 10	0–25
Psychological Dysfunction	14, 15, 16, 17, 18, 19, 20	0–35
Sleep Dysfunction	11, 12, 13, 14, 15	0–25

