9.5 Secondary Endpoint Analysis

Secondary endpoints to be collected and analyzed are listed below alongside references to the sections in which they are defined:

CT grading by an independent, blinded reviewer (see Section 9.2.1):

- Cross-sectional area of FSO (Day 180) and change from baseline
- FSOT volume (Day 180) and change from baseline
- FSO minimum diameter (Day 180) and change from baseline
- Zinreich's modified Lund-Mackay score for the frontal sinus (change from baseline to Day 45)
- Zinreich's modified Lund-Mackay score for the frontal sinus (Day 180) and change from baseline
- Lund-Mackay score for the frontal sinus (Day 45, 180) and change from baseline

CT grading by clinical investigators (see Section 9.2.1):

- Lund-Mackay score for the frontal sinus (Day 45, 180) and change from baseline

Endoscopic grading by clinical investigators (see Section 9.2.2):

- Need for post-operative intervention in the frontal recess/FSO as determined by clinical investigators (Day 21, 90, 180)
- Adhesion/scarring grade in the frontal recess/FSO (Day 21, 45, 90, 180):
- Adhesion/scarring grade in the ethmoid sinus (Day 21, 45, 90, 180):
- Inflammation score in the frontal recess/FSO (Day 21, 45, 90, 180):
- Polypoid edema in the frontal recess/FSO (Day 21, 45, 90, 180):

Patient-reported outcomes (see Section 9.2.4):

- CRS side-specific questionnaire (Day 21, 45, 90, 180)
- SNOT-22 score (Day 180)
- RSI score (Day 180)

Implant delivery success rate (see Section 9.2.5)

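### Under SAP 9.1, one blank item makes a whole SNOT-22 or RSI total missing, and no proration rule or scheduled earlier value can recover it

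*SAP*

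**What the plan says.** SAP 6.7 sends missing efficacy data to the rules elsewhere in the plan: "Missing data for each efficacy endpoint will be handled as described in Sections 9.1 and 9.3.4". The observed-case rule in SAP 9.1 reads "For continuous composite endpoints, if any components are missing, the composite endpoints will be set as missing".

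SAP 6.1 classes the questionnaire scores as continuous: "CRS side-specific symptom score, SNOT-22 score, and RSI score will be summarized in terms of the mean". SAP 9.2.4.1 defines the SNOT-22 total: "The total score is calculated as the sum of all 22 items". SAP 9.2.4.2 defines the RSI total in the same way over 12 symptoms. Neither section says how to score a partly answered form.

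The default in SAP 6.1 is "No imputations for missing data are planned, unless indicated otherwise". SAP 9.1 also describes an LOCF variant, but with the limit "Baseline measurements will not be carried forward to post-baseline", and any component still missing after LOCF returns to the observed-case rule. The SAP does not say which variant applies to SNOT-22 and RSI.

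The schedules of assessments (Protocol section 7, SAP Appendix A) place both questionnaires at baseline and Day 180 only. SAP 6.7 adds that a missing baseline value is not imputed and that the endpoint is then missing at every visit.

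**The concern.** A subject who answers 21 of 22 SNOT-22 items has given nearly all the information in the score, yet the rule treats that form as if it had never been returned. The more items a score has, the more likely it is to be lost.

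The same paragraph of SAP 9.1 is more forgiving to categorical composites, which are derived from whatever components are present when these suffice. No reason is given for the difference.

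The loss can occur twice. A blank item at baseline makes the baseline total missing, and SAP 6.7 then removes the Day 180 total even if that form is complete. Domain scores are exposed too: in SAP Table 3, items 2, 6, 14 and 15 each belong to two SNOT-22 domains, so one blank there removes two domains and the total.

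At stake are the precision of the patient-reported summaries and, if subjects who skip items differ from those who do not, how well the summaries represent the trial population.

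**Working it through.** The documents state no skip rate and no expected loss of questionnaire totals, so there is no figure of the plan's own to reproduce. The skip rate q below is an assumption, shown over a range.

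**Inputs from the documents**
- Items per total: SNOT-22 k = 22 (SAP 9.2.4.1); RSI k = 12 (SAP 9.2.4.2).
- SNOT-22 at Day 180 with a complete baseline also required (SAP 6.7): k = 22 + 22 = 44.
- Planned randomized subjects: 80 (SAP 4.4).

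**Step 1: independent skips.** P(total missing) = 1 − (1 − q)^k.

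| Score | k | q = 0.1% | q = 0.5% | q = 1% | q = 2% |
|---|---|---|---|---|---|
| SNOT-22, Day 180 | 22 | 2.2% | 10.4% | 19.8% | 35.9% |
| RSI, Day 180 | 12 | 1.2% | 5.8% | 11.4% | 21.5% |
| SNOT-22, Day 180 with baseline | 44 | 4.3% | 19.8% | 35.7% | 58.9% |

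For example, 1 − 0.99^22 = 0.198. If all 80 subjects returned a Day 180 form, 80 × 0.198 ≈ 16 totals would be lost. With baseline also required, 80 × 0.357 ≈ 29.

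**Step 2: bounds at q = 1%, whatever the dependence.** If the same subjects skip every item, the loss equals q = 1%. If skips never fall on the same subject, it is k × q = 22 × 1% = 22%. Day 180 SNOT-22 loss therefore lies between 1% and 22%, and independence is close to the top. On 44 items the upper bound is 44 × 1% = 44%.

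**Step 3: partial clustering at q = 1%.** In a beta-binomial model with within-subject correlation ρ, set s = 1/ρ − 1, a = q·s and b = (1 − q)·s. Then P(total missing) = 1 − B(a, b + k)/B(a, b), where B is the beta function.

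| ρ | 22 items | 44 items |
|---|---|---|
| 0.05 | 13.9% | 20.7% |
| 0.1 | 10.9% | 15.1% |
| 0.3 | 5.8% | 7.2% |

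**Step 4: can LOCF recover the total?** The only scheduled value before Day 180 is baseline, which SAP 9.1 bars from being carried forward. Protocol 12.5 makes the questionnaires optional at unscheduled visits, so an earlier post-baseline value would exist only by chance.

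**The case against.** **The rule reaches these scores by inference.** The SAP never calls SNOT-22 or RSI composite; where it names a composite (SAP 9.8) it means post-operative intervention. This is fair. But summed questionnaires are the evident continuous endpoints with components, and if 9.1 was not meant for them, a partly answered form has no scoring rule at all. One is needed on either reading.

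**The side-specific symptom score.** A reader might infer that the CRS side-specific score suffers in the same way, with ten items needed per subject per visit. The documents do not support that. SAP 9.2.4.3 has each symptom scored by side and defines no sum, and the four post-baseline visits would let component-level LOCF fill gaps after Day 21.

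**Mailed forms.** A reader might infer that home completion makes skipped items likely. Protocol 21.1 does say "The study staff can mail the paper questionnaires", but as a COVID-19 contingency, with the form completed during a virtual visit. The protocol also provides for checks on omitted data with site queries (19.7) and monitoring of completeness (19.6). Nothing in the documents shows that skipping will be common.

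**The 44-item figure.** SAP 9.5 lists SNOT-22 at Day 180 without change from baseline, which it does add for the CT rows. The figure stands all the same, because it rests on the missing-baseline rule in SAP 6.7 and not on a change score.

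**Complete-item scoring is a legitimate prespecified choice, and the consequence is small.** The second part stands. SNOT-22 and RSI describe the whole subject and cannot compare the two sides. SAP Table 2 puts them in the PTE population only, and SAP 9.4.1 treats secondary endpoints outside the five key ones as exploratory or explanatory. SNOT-22 domains of 3 to 7 items lose only about 3% to 7% at a 1% skip rate under independence (1 − 0.99^3 and 1 − 0.99^7). The first part is true, but the choice discards answered items for no stated reason.

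**Conclusion.** The concern holds for the SNOT-22 and RSI totals as a minor, cheaply corrected loss of precision. At an assumed 1% skip rate, a plausible loss of Day 180 SNOT-22 totals is about 6% to 14% with moderate clustering (ρ from 0.3 to 0.05) and 19.8% with none. The missing-baseline rule can raise the independent figure to about 36%.

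This rests on two assumptions: that 9.1 covers summed questionnaires, and a skip rate that the documents do not supply. Loss of a fifth might be read as a forecast or as the worst case. It is neither: it is the independence value at one assumed rate, within bounds of 1% to 22% for the Day 180 items alone. Nor does the point extend to the CRS side-specific score or to the primary and key secondary results.

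**What to change.** In SAP 9.1 and 9.2.4, name SNOT-22 and RSI and give them a scoring rule for partly answered forms:
- When at least half the items are answered (11 of 22 for SNOT-22, 6 of 12 for RSI), the total is the mean of the answered items times the number of items. Otherwise it is missing.
- The same rule applies to domains of three or more items.
- The two-item RSI systemic domain keeps complete-item scoring, because prorating it would let a fever answer stand in for fatigue, or the reverse.
- The rule applies at baseline and at follow-up, so that one blank baseline item no longer removes Day 180 through SAP 6.7.

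The cost is a sentence or two in the SAP and a scoring line in the program. Proration assumes that skipped items resemble answered ones. The half-item threshold is a choice that the documents do not supply, and forms more than half blank stay missing. Under SAP 6.1 the change counts as a priori only if made before database lock and review of unblinded results, so it should precede the Day 45 unblinding in SAP 5.2. Type I error control for the primary and the five key secondary tests is untouched.
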